7.2 Exclusion Criteria

- 1. Known prior progression to AML, defined by at least 20% blasts in the blood or bone marrow.
- 2. Myelodysplastic or myeloproliferative syndrome other than MDS.
- 3. More than two prior systemic regimens for MDS. Prior systemic regimens are those that are considered standard of care for the treatment of MDS, have been received at standard doses for at least one full treatment cycle and exclude ESA.
- 4. Prior cytoreductive therapy for blast reduction.
- 5. Participation in any interventional study within 1 week or 5 half lives (whichever is longer) of Cycle 1 Day 1.
- 6. Ongoing treatment with an anticancer agent for MDS not contemplated in this protocol.
- 7. Prior treatment (at least 1 full treatment cycle) with a farnesyltransferase inhibitor.
- 8. Clinically significant anemia due to iron, B12, or folate deficiencies, or autoimmune or hereditary hemolytic anemia, or gastrointestinal bleeding. If marrow stain for iron is not available, the transferrin saturation (iron/total iron binding capacity Fe/TIBC) must be >20% or serum ferritin must be >100 ng/dL.

- 9. Active coronary artery disease requiring treatment, myocardial infarction within the prior year, New York Heart Association grade III or greater congestive heart failure, cerebrovascular attack within the prior year, or current serious cardiac arrhythmia requiring medication except atrial fibrillation.
- 10. Major surgery, other than diagnostic surgery, within 2 weeks prior to Cycle 1 Day 1, without complete recovery.
- 11. Active, concurrent malignancy requiring radiation, chemotherapy, or immunotherapy (excluding non-melanoma skin cancer, adjuvant hormonal therapy for breast cancer and hormonal treatment for castration sensitive prostate cancer).
- 12. Active, uncontrolled bacterial, viral, or fungal infections, requiring systemic therapy. Known infection with human immunodeficiency virus (HIV), or an active infection with hepatitis B or hepatitis C.
- 13. Subjects who have exhibited allergic reactions to tipifarnib, or structural compounds similar to tipifarnib or to its excipients.
- 14. Concomitant disease or condition that could interfere with the conduct of the study, or that would, in the opinion of the investigator, pose an unacceptable risk to the subject in this study.
- 15. The subject has legal incapacity or limited legal capacity.

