9.11 Prior and Concomitant Medications

All prescription and over-the-counter medications taken by a subject within 28 days before the first study drug administration will be recorded in the CRF. In particular, subjects will be asked about the use of agents that may affect the mevalonate pathway including statins (e.g. atorvastatin, simvastatin, rosuvastatin, pravastatin), bisphosphonates (e.g. pamidronate, risedronate, ibandronate, etidronate, alendronate) and nutritional agents (e.g. coenzyme Q_{10} , ubiquinone). Any additional concomitant therapy that becomes necessary during the study and any change to concomitant drugs must be recorded in the corresponding section of the CRF, noting the name, dose, duration and indication of each drug.

Supportive care medications considered necessary for the subject's safety and well-being may be given at the discretion of the Investigator according to local guidelines and standard practices. For concomitant therapy given as a treatment for a new condition or a worsening of an existing condition, the condition must be reported on the AE form of the CRF.

Subjects may use proton pump inhibitors or H2 antagonists during the treatment portion of this study. However, subjects should be instructed to use antacids (magnesium or aluminum containing products) at least 2 hours before or after intake of oral study drug.

Corticosteroids (up to 10 mg prednisone daily or its equivalent) may be administered for concomitant medical conditions.

Any additional concomitant therapy that becomes necessary during the study and any change to concomitant drugs must be recorded in the corresponding section of the CRF, noting the name, dose, duration and indication of each drug.

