11 STUDY PROCEDURES

11.1 Screening and Baseline Assessments

A signed Informed Consent Form (ICF) must be obtained before any study-specific screening evaluations are performed and should be documented in the subject's medical chart.

The following evaluations and procedures will be performed within 28 days prior to the first study drug administration (Cycle 1 Day 1). Any screening evaluation, including disease status, will need to be repeated if performed more than 28 days from Cycle 1 Day 1. Evaluations performed as part of the standard of care within 28 days of dosing but prior to consent, do not need to be repeated. By signing the consent form, the subject agrees to the collection of this health information.

- Obtain signed ICF and form for the HIPAA/Data Protection Act
- Record subject's medical history, including demographics, primary diagnosis and WHO
 classification (Table 8), outcome and duration of response to prior cancer therapy and any
 ongoing AEs
- Record the number of RBC, whole blood and platelet transfusions for the 4 months prior to Cycle 1 Day 1.
- Record concomitant medications
- Record subject height

- Perform hematology tests: hemoglobin, reticulocytes, platelets, WBCs, neutrophils, neutrophil precursors (promyelocytes, myelocytes, metamyelocytes, band neutrophils), monocytes, lymphocytes and blasts. Hematology tests must be performed ≥ 1 week prior to Cycle 1 Day 1.
- Perform serum chemistry laboratory tests (AST, ALT, total bilirubin, creatinine, BUN, potassium and calcium). Subjects are not required to be fasting.
- Perform coagulation tests (APTT, PT/INR)
- Perform bone marrow aspirate for disease assessment,
 If the bone marrow aspirate is inadequate, a bone marrow biopsy should be performed.

The following evaluations and procedures will be performed within 14 days prior to the first administration of study drug (Cycle 1 Day 1):

- Record subject weight
- Collect vital signs (heart rate, blood pressure, temperature)
- Complete physical examination
- Assess ECOG performance status.

The following evaluation and procedure must be performed within 72 hours prior to the first administration of study drug (Cycle 1 Day 1):

Perform urine or serum pregnancy test for females of child-bearing potential only

Laboratory assessments may be repeated if values are borderline to inclusion level or may change due to best supportive care measures.

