12.2 Endpoints

12.2.1 Efficacy

Disease response assessment will be performed by the Investigator according to the MDS IWG criteria (Table 9 and Table 10).

For the evaluation of the primary endpoint (i.e. ORR) to determine advancement to the second stage of the study (i.e. enrollment of 7 additional subjects in the dose regimen cohort) and overall outcome of the study, each dose regimen cohort will be evaluated independently.

Transfusion independence and disease response will be summarized descriptively per dose regimen cohort and overall.

The objective response rate will be estimated and includes the following response types: CR, PR, marrow CR and HI according to the MDS IWG criteria (Table 9 and Table 10). The estimate of the objective response rate will be calculated based on the maximum likelihood estimator (i.e., crude proportion of subjects whose best overall response is CR, PR, marrow CR or HI). The estimate of the objective response rate will be accompanied by 2-sided 95% exact binomial confidence intervals.

The duration of objective response will be calculated for subjects who achieve CR, PR, marrow CR or HI. For such subjects, the duration of objective response is defined as the number of days from the start date of response (whichever response is achieved first) to the first date that progressive disease is objectively documented. Disease progression will be determined by the Investigator using MDS IWG criteria (Table 10). The duration of objective response will be right-censored for subjects who achieve a response and meet 1 of the following conditions: 1) non-protocol anticancer treatment started before documentation of disease progression, 2) death or documented disease progression after more than 1 missed disease assessment visit, or 3) alive and does not have documentation of disease progression before a data analysis cutoff date.

The duration of objective response will be summarized descriptively using the Kaplan-Meier method. The 50th percentile of the Kaplan-Meier distribution will be used to estimate the median response duration.

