Progression free survival will be defined as the time (in months) from enrollment to either first observation of progressive disease or occurrence of death due to any cause within 1 year (approximately 4 time intervals for disease assessments) of either first administration of tipifarnib or the last disease assessment. Similarly, survival will be defined as the time (in months) from enrollment to occurrence of death due to any cause within 1 year (approximately 4 time intervals for disease assessments) of either first administration of tipifarnib or the last disease assessment

Determination of RBC TI will be assessed by the Investigator through the review of subject transfusion requirements and hemoglobin levels. RBC TI will be defined as the absence of the intravenous infusion of any RBC transfusion during any consecutive "rolling" 56 days during the treatment period, i.e. days 1 to 56, days 2 to 57, days 3 to 58, etc. and a \geq 1 g/dL increase in hemoglobin level. The rise in the hemoglobin concentration in subjects who no longer require transfusions will be calculated as the difference between the maximum hemoglobin concentration and the minimum pre-transfusion value during the 12 weeks before enrollment in the study.

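### The ferritin limit in the no-stain fallback of exclusion 8 is printed in ng/dL, so it equals 1 ng/mL and, applied literally, leaves that fallback almost no screening value

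*Protocol*

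**What the plan says.** Exclusion 8 appears with the same wording in the Protocol synopsis and in section 7.2. It has two parts.

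- **Opening sentence.** It bars "Clinically significant anemia due to iron, B12, or folate deficiencies", as well as hemolytic anemia and gastrointestinal bleeding. It does not depend on any ferritin value.
- **Fallback.** "If marrow stain for iron is not available, the transferrin saturation" "must be >20% or serum ferritin must be >100 ng/dL". Meeting either limit is enough.

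The following passages bear on the effect of the fallback:

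- Section 11.1 plans a marrow sample for every subject at screening: "Perform bone marrow aspirate for disease assessment". The readable text does not name an iron stain.
- The screening chemistry line reads "Perform serum chemistry laboratory tests (AST, ALT, total bilirubin, creatinine, BUN, potassium and calcium". Ferritin, serum iron and iron-binding capacity are not listed there, in section 10.14, or in the laboratory note to the schedule of activities.
- Section 12.2.1 defines an objective response rate that "includes the following response types: CR, PR, marrow CR and HI". For red-cell transfusion independence it says "Determination of RBC TI will be assessed by the Investigator through the review of subject transfusion requirements and hemoglobin levels", and a hemoglobin rise of at least 1 g/dL is required.
- Section 9.11 says "Supportive care medications considered necessary for the subject's safety and well-being may be given at the discretion of the Investigator". Section 9.12 does not list iron among the treatments not permitted.
- Protocol section 12.1.1 and SAP section 6 remove from the FAS any subject who did not meet the Amendment 3 eligibility criteria.

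**The concern.** The fallback is the only numerical iron test the protocol gives for a subject without a marrow stain. At 1 ng/mL the ferritin limit would be passed by nearly any measurable value, if local lower normal limits are in the range assumed here. Since ferritin alone is enough, a low transferrin saturation would then not exclude the subject.

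Two consequences follow. First, sites may read the unit differently: one may convert it literally, another may assume ng/mL. The same subject could then be eligible at one site and ineligible at another, and in or out of the FAS accordingly. Second, a subject with unrecognised iron deficiency may gain hemoglobin from iron given as supportive care. That gain could be scored as HI, which counts in the primary ORR, and could contribute to the hemoglobin part of transfusion independence. Each cohort is judged on 2 responses of 11 and then 4 of 18, so a single misattributed response carries weight.

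**Working it through.** **1. The unit.** One dL is 100 mL, so 100 ng/dL ÷ 100 = 1 ng/mL. The documents give no laboratory reference range. Assuming a lower normal limit of 10 to 30 ng/mL, the printed limit is lower by a factor of 10/1 = 10 to 30/1 = 30. If ng/mL was meant, the printed limit is too low by a factor of 100.

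**2. The logic.** Take an invented subject without an iron stain, with ferritin 8 ng/mL and transferrin saturation 6%.

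| Reading of the ferritin limit | Ferritin test | Saturation test (>20%) | Fallback |
|---|---|---|---|
| Literal: >100 ng/dL = >1 ng/mL | 8 > 1, passes | 6% fails | Met |
| Read as >100 ng/mL | 8 < 100, fails | 6% fails | Not met |

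This table concerns the fallback only. If the investigator attributes clinically significant anemia to iron deficiency, the opening sentence excludes the subject under either reading.

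**3. The plan's own design figures.** The inputs come from Protocol section 12 (sample size) and SAP section 5: 11 subjects per cohort in stage 1, continue with at least 2 responses, add 7, and call the cohort positive with at least 4 of 18, for 10% against 30%. With B(n, p) a binomial count,

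P(positive) = Σ over x ≥ 2 of P(B(11, p) = x) × P(B(7, p) ≥ 4 − x).

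At p = 0.10:

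- x = 2: 0.2131 × 0.1497 = 0.0319
- x = 3: 0.0710 × 0.5217 = 0.0371
- x ≥ 4: 0.0185
- Sum: 0.0875 (stated 0.087)

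At p = 0.30 the same formula gives 0.800 (stated 80%). The probability of stopping after stage 1 is 0.697 at 10% and 0.113 at 30%, both as stated. The design figures reproduce and are not in question.

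**4. Worst-case illustration.** Suppose exactly one subject in a cohort is certain to be scored as a responder because of iron repletion, and every other subject responds with probability 0.10.

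*Subject in stage 1.* The other 10 need at least 1 response to continue and, with stage 2, at least 3 in total:

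- x = 1: 0.3874 × 0.1497 = 0.0580
- x = 2: 0.1937 × 0.5217 = 0.1011
- x ≥ 3: 0.0702
- Sum: 0.229

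*Subject in stage 2.* Stage 1 needs at least 2 of 11, and the remaining 6 subjects in stage 2 must bring the total without the certain responder to at least 3:

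- x = 2: 0.2131 × 0.4686 = 0.0998
- x ≥ 3: 0.0896
- Sum: 0.189

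Averaged over the 18 positions: (11 × 0.229 + 7 × 0.189)/18 = 0.214.

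**The case against.** The strongest reply is that this is probably a unit slip in a clause that seldom operates. Much of that stands.

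- **Iron-deficiency anemia is still excluded.** A reader might infer from the unit that such anemia may freely enter the trial, or that exclusion 8 as a whole excludes almost nobody. The documents do not support either reading, because the opening sentence applies whatever the ferritin value. What remains is deficiency that goes unrecognised in a subject judged on the fallback alone.
- **The fallback is narrow.** Every subject has a screening marrow sample, and a biopsy if the aspirate is inadequate. The readable text names no iron stain, but part of the aspirate line in section 11.1 is missing, so nothing can be concluded from that silence. That the protocol has a fallback shows that missing stains were foreseen, not how often they occur.
- **The word 'or' is not an error.** Accepting either of two pieces of evidence is a normal rule. It matters here only because the printed ferritin limit is so low.
- **The route to a false response has several steps.** There must be no stain, unrecognised deficiency, a literal reading of the unit, iron given on study, a sufficient hemoglobin rise, and an investigator who scores it as HI. The documents give no frequency for any of these, and the HI criteria table is not readable in the public text. If iron is given, someone may well have recognised the deficiency.
- **The effect on the decision is easily overstated.** A reader might turn one extra responder into a common rate of 0.10 + 0.90/18 = 0.15, or about 0.155, and obtain 0.254 to 0.274. That raises the response probability of all 18 subjects, which is a different scenario. With one fixed responder the figures are 0.189 and 0.229.

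The reply does not remove the printed limit itself. It is an operative eligibility threshold, it appears in both places, and nothing in the documents lets a site recover another unit.

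**Conclusion.** The point holds for the no-stain fallback only. The 1 ng/mL equivalence is plain arithmetic. That the fallback then screens out almost nobody rests on the assumed lower normal limits of 10-30 ng/mL. For subjects without a stain whose deficiency is not otherwise recognised, the reading of the unit can settle both eligibility and FAS membership. How many subjects that is cannot be found from the documents.

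The rise in the chance of a positive cohort from 0.087 to 0.19-0.23 is a worst-case bound for one certain responder at a true ORR of 10%. It is not an estimate of bias, and the stated error rate and power of the design are unaffected. It is likewise not established that ng/mL was intended: ng/dL appears to be an error by a factor of 100 if so, but the documents never state ng/mL. The item is worth correcting because it is an operative cut-off and the correction costs almost nothing.

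**What to change.** The sponsor should confirm the intended ferritin unit, correct exclusion 8 identically in the synopsis and section 7.2, and confirm that 'or' between the two tests is intended once the unit is settled. Which limit is clinically right is for the sponsor to say, and none is proposed here.

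For any subject already admitted through the fallback, eligibility should be checked against the confirmed unit before FAS membership is fixed. The cost is a wording correction in two places at the next amendment and, where it applies, a check of existing screening records. No change to the design or sample size is needed.

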8 TRIAL DESIGN

8.1 Study Design

This phase 2 study will investigate the antitumor activity in terms of ORR of tipifarnib in approximately 36 eligible subjects with MDS who have no known curative treatment.

A two-stage study design was selected in order to minimize the number of study subjects treated if tipifarnib were considered not sufficiently efficacious to grant further development in this subject population. This design is intended to allow the termination of accrual in case of unacceptably low efficacy as measured by ORR.

In the first stage, 22 eligible subjects will be enrolled and randomized in to one of two dose regimen cohorts (11 subjects per cohort). If two or more responses are observed in a given dose regimen cohort, 7 additional study subjects will be enrolled. Each dose regimen cohort is designed to test the null hypothesis of ORR rate less than 10% vs alternative hypothesis of ORR rate at least 30% and will be evaluated independently. At the completion of the study, treatment will be considered of further interest if the true ORR rate is higher than 10% (at least 4

responders out of 18 subjects in a dose regimen cohort). This design provides 80% power to detect a difference between 10% and 30% ORR rate at one-sided significance level of 0.087.

Only consented subjects who meet all eligibility criteria will be enrolled in the study. Screening evaluations will be completed within 4 weeks (28 days) of Cycle 1 Day 1. Any screening evaluation, including disease status, will need to be repeated if performed more than 4 weeks from Cycle 1 Day 1. Evaluations performed as part of the standard of care within 28 days of dosing but prior to consent, do not need to be repeated. By signing the consent form, study subjects agree to the collection of standard of care health information.

Subjects will be randomized to receive tipifarnib orally with food, twice a day (bid) according to one of the following dose regimens:

• Regimen 1: 600 mg bid for 7 days on Days 1-7 in 28 day cycles (i.e. 1 week on / 3 weeks off).

At the discretion of the investigator, the dose of tipifarnib may be increased to 800 mg bid if the subject has not experienced dose limiting toxicities at the 600 mg dose level. Subjects are not to be dose escalated until after completing Cycle 1 to ensure the dosing regimen is tolerated prior to escalation. Subjects who develop serious adverse events, \geq grade 2 TEAEs that are deemed related to tipifarnib and lasting \geq 14 days will not undergo dose escalation. Stepwise 200 mg dose reductions to control treatment-related, treatment-emergent toxicities are also allowed. Subjects who develop serious adverse events (SAE), \geq grade 2 treatment-emergent adverse events (TEAE) that are deemed related to tipifarnib and lasting \geq 14 days will not undergo dose escalation.

• Regimen 2: 300 mg bid for 21 days on Days 1-21 in 28 day cycles (i.e. 3 weeks on / 1 week off).

Stepwise 100 mg dose reductions to control treatment-related, treatment-emergent toxicities are allowed.

Subjects who received a starting dose of 900 mg bid during the conduct of the original version of this protocol may be dose reduced to the 600 mg bid dose at the discretion of the investigator. Subjects who received tipifarnib on Days 1-7 and Days 15-21 during the conduct of the original version and amendment 1 of this protocol, may transition to the new treatment administration schedule (tipifarnib on Days 1-7 in 28 day cycles) beginning on Day 1 of their next cycle.

Subjects may use proton pump inhibitors or H2 antagonists during the treatment portion of this study. However, subjects should be instructed to use antacids (magnesium or aluminum containing products) at least 2 hours before or after intake of oral study drug.

In the absence of unmanageable toxicities, subjects may continue to receive tipifarnib treatment until disease progression. If a complete remission is observed, therapy with tipifarnib will be maintained for at least 6 months beyond the start of response.

Hematologic assessments, including peripheral blood evaluations and review of transfusion requirements, will be performed at screening and at least monthly until disease progression. Disease assessments will also be performed at screening and at least once every approximately 12 weeks starting at the end of cycle 3. As part of the disease assessment at screening and during Cycles 3, 6 and 9, bone marrow evaluation will be performed. Thereafter, bone marrow evaluations will occur during disease assessments in accordance with institutional standard practice. Additional hematologic or disease assessments may be conducted if deemed necessary by the Investigator. The timing of the hematologic and disease assessments should be maintained as much as possible independently of potential treatment cycle delays.

Determination of ORR will be assessed by the Investigator according to the MDS IWG criteria (Table 9 and Table 10).

Upon disease progression, all subjects in the study cohort will be followed approximately every 12 weeks for survival and the use of subsequent therapy until either death or 12 months after accrual of the study cohort has been completed, whichever occurs first. Information on survival and subsequent anticancer therapy may be collected by phone.

Subjects who terminate treatment for reasons other than death or disease progression will be assessed at regular intervals for disease progression (approximately every 12 weeks) and leukemic transformation (monthly blood counts). Disease assessments performed during the first 9 months from the start of the subject's participation in the study will include bone marrow evaluation. Thereafter, bone marrow evaluations will occur during disease assessments in accordance with institutional standard practice. These assessments will continue until disease progression, withdrawal of subject's consent to study procedures or initiation of another anticancer therapy.

All subjects will be followed-up for safety during treatment and up to approximately 30 days (30 \pm 7 days) after treatment discontinuation or until immediately before the initiation of another anticancer therapy, whichever occurs first. Additional follow up may be implemented until the subject recovers from any emergent treatment related toxicity or the adverse event is considered irreversible by the Investigator. Target organ toxicities will be monitored via clinical and laboratory assessments using the NCI CTCAE v.4.03 criteria.

